7.2.2. Assessment of Severity

Severity of adverse events is to be determined based on GSI Grading Scale for Severity of Adverse Events and Laboratory Abnormalities ([Appendix 5](#)). A distinction should be drawn between seriousness and severity of AEs. An AE that is assessed as Grade 4 (potentially life-threatening) should not be confused with an SAE. Severity is a category utilized for rating the intensity of an event: both AEs and SAEs can be assessed as Grade 4. An event is defined as “serious” when it meets one of the predefined outcomes described above in Section [7.2](#).

7.3. Investigator Requirements and Instructions for Reporting Adverse Events and Serious Adverse Events to Gilead or CRO

Requirements for collection prior to study drug initiation:

After informed consent, but prior to initiation of study medication, the following types of events should be reported on the case report form (CRF/eCRF): all serious adverse events (SAEs) and adverse events related to protocol-mandated procedures.

Adverse Events

Following initiation of study medication, collect all AEs, regardless of cause or relationship, until 4-weeks after last administration of study IMP. AEs must be reported to the CRF/eCRF database as instructed.

All AEs should be followed up until resolution or until the AE is stable, if possible. Gilead Sciences may request that certain AEs be followed beyond the protocol defined follow up period.

Serious Adverse Events

All SAEs, regardless of cause or relationship, that occur after the subject first consents to participate in the study (ie, signing the informed consent) and throughout the duration of the study, including the protocol-required post treatment follow-up period, must be reported to the CRF/eCRF database and Gilead Drug Safety and Public Health (DSPH) as instructed. This also includes any SAEs resulting from protocol-associated procedures performed after informed consent is signed. Any SAEs and deaths, regardless of causality, that occur during the post treatment follow-up period or within 30 days of the last dose of study drug, when subject transitions to alternative, commercially available HBV therapy, should also be reported.

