Proteinuria (Dipstick)	1+	2-3+	4+	NA
Proteinuria, 24 Hour Collection Adult and Pediatric ≥ 10 Years Pediatric > 3 Mo to < 10 Years	200 to 999 mg/24 h	> 999 to 1999 mg/24 h	> 1999 to 3500 mg/24 h	> 3500 mg/24 h
	201 to 499 mg/m ² /24 h	> 499 to 799 mg/m ² /24 h	> 799 to 1000 mg/m ² /24 h	> 1000 mg/m ² /24 h
Glycosuria (Dipstick)	1+	2-3+	4+	NA

Note: Toxicity grades for Quantitative and Dipstick Hematuria will be assigned by Covance Laboratory, however for other laboratories, toxicity grades will only be assigned to Dipstick Hematuria.

With the exception of lipid tests, any graded laboratory test with a result that is between the LLN and ULN should be assigned Grade 0.

If the severity of a clinical AE could fall under either one of two grades (e.g., the severity of an AE could be either Grade 2 or Grade 3), select the higher of the two grades for the AE.

CARDIOVASCULAR				
	Grade 1	Grade 2	Grade 3	Grade 4
Cardiac Arrhythmia (general) (By ECG or physical exam)	Asymptomatic AND No intervention indicated	Asymptomatic AND Non-urgent medical intervention indicated	Symptomatic, non-life-threatening AND Non-urgent medical intervention indicated	Life-threatening arrhythmia OR Urgent intervention indicated
Cardiac-ischemia/Infarction	NA	NA	Symptomatic ischemia (stable angina) OR Testing consistent with ischemia	Unstable angina OR Acute myocardial infarction
Hemorrhage (significant acute blood loss)	NA	Symptomatic AND No transfusion indicated	Symptomatic AND Transfusion of ≤ 2 units packed RBCs (for children ≤ 10 cc/kg) indicated	Life-threatening hypotension OR Transfusion of > 2 units packed RBCs indicated (for children ≤ 10 cc/kg) indicated
Hypertension (with repeat testing at same visit)	$> 140\text{--}159$ mmHg systolic OR $> 90\text{--}99$ mmHg diastolic	$> 159\text{--}179$ mmHg systolic OR $> 99\text{--}109$ mmHg diastolic	> 179 mmHg systolic OR > 109 mmHg diastolic	Life-threatening consequences (e.g., malignant hypertension) OR Hospitalization (other than ER visit) indicated
Pediatric ≤ 17 Years (with repeat testing at same visit)	NA	91st–94th percentile adjusted for age, height, and gender (systolic and/or diastolic)	≥ 95 th percentile adjusted for age, height, and gender (systolic and/or diastolic)	Life-threatening consequences (e.g., malignant hypertension) OR Hospitalization indicated (other than emergency room visit)

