Seizure – Pediatric < 18 Years	Seizure, generalized onset with or without secondary generalization, lasting < 5 minutes with < 24 hours post ictal state	Seizure, generalized onset with or without secondary generalization, lasting 5–20 minutes with < 24 hours post ictal state	Seizure, generalized onset with or without secondary generalization, lasting > 20 minutes	Seizure, generalized onset with or without secondary generalization, requiring intubation and sedation
Syncope (not associated with a procedure)	NA	Present	NA	NA
Vertigo	Vertigo causing no or minimal interference with usual social & functional activities	Vertigo causing greater than minimal interference with usual social & functional activities	Vertigo causing inability to perform usual social & functional activities	Disabling vertigo causing inability to perform basic self-care functions

MUSCULOSKELETAL				
	Grade 1	Grade 2	Grade 3	Grade 4
Arthralgia See also Arthritis	Joint pain causing no or minimal interference with usual social & functional activities	Joint pain causing greater than minimal interference with usual social & functional activities	Joint pain causing inability to perform usual social & functional activities	Disabling joint pain causing inability to perform basic self-care functions
Arthritis See also Arthralgia	Stiffness or joint swelling causing no or minimal interference with usual social & functional activities	Stiffness or joint swelling causing greater than minimal interference with usual social & functional activities	Stiffness or joint swelling causing inability to perform usual social & functional activities	Disabling joint stiffness or swelling causing inability to perform basic self-care functions
Bone Mineral Loss Pediatric < 21 Years	BMD t-score or z-score -2.5 to -1.0 BMD z-score -2.5 to -1.0	BMD t-score or z-score -2.5 to -1.0 BMD z-score < -2.5	Pathological fracture (including loss of vertebral height) Pathological fracture (including loss of vertebral height)	Pathologic fracture causing life-threatening consequences Pathologic fracture causing life-threatening consequences
Myalgia (non-injection site)	Muscle pain causing no or minimal interference with usual social & functional activities	Muscle pain causing greater than minimal interference with usual social & functional activities	Muscle pain causing inability to perform usual social & functional activities	Disabling muscle pain causing inability to perform basic self-care functions

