7.1.2. Adverse Event Severity

AEs are graded by the investigator as Grade 1 (mild), Grade 2 (moderate), Grade 3 (severe) or Grade 4 (life threatening) according to toxicity criteria specified in Appendix 5 of the clinical study protocol. The severity grade of events for which the investigator did not record severity will be categorized as “missing” for tabular summaries and data listings, and will be considered the least severe for the purposes of sorting for data presentation.

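### The adult bone mineral loss line of the severity scale uses one score range for both Grade 1 and Grade 2 and has no non-fracture grade below -2.5

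*Protocol*

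**What the plan says.** Both documents make Appendix 5 the operative scale. Protocol 7.2.2 states: "Severity of adverse events is to be determined based on GSI Grading Scale for Severity of Adverse Events and Laboratory Abnormalities". SAP 7.1.2 has the investigator grade each event on that appendix: "AEs are graded by the investigator as Grade 1 (mild), Grade 2 (moderate), Grade 3 (severe) or Grade 4 (life threatening".

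The Bone Mineral Loss row is in the Musculoskeletal block of Appendix 5. Each of its cells holds an adult line followed by a line for subjects under 21:

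- Grade 1: "BMD t-score or z-score -2.5 to -1.0 BMD z-score -2.5 to -1.0"
- Grade 2: "BMD t-score or z-score -2.5 to -1.0 BMD z-score < -2.5"
- Grade 3: "Pathological fracture (including loss of vertebral height"), the same on both lines
- Grade 4: "Pathologic fracture causing life-threatening consequences", the same on both lines

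A note placed before the clinical blocks of the scale gives a tie rule. It begins "If the severity of a clinical AE could fall under either one of two grades" and tells the grader to "select the higher of the two grades for the AE".

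SAP 7.1.2 shows an event with no recorded severity as missing in tables and listings, and ranks it lowest when sorting. SAP 7.1.7 plans summaries of AEs of Grade 2, 3 or 4, which become Tables 26 (overall summary), 29 (all such AEs) and 32 (drug-related).

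**The concern.** A severity scale has to give each event one grade, and a worse finding should not fall off the scale. The adult line fails on both counts. Two adjacent grades share one range, and the range below it, down to fracture, belongs to none.

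What is at stake is the split of bone-loss AEs by severity. AEs with milder scores are pushed into the Grade 2, 3 or 4 counts. AEs with worse scores depend on what each site decides to enter when the scale offers nothing. The SAP foresees such events: its bone-event list (Appendix 3) includes terms for reduced bone density, osteopenia and osteoporosis.

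**Working it through.** No sample size, power or error rate is involved, and the plan states no figure to reproduce. The check is to map scores to grades from the text.

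**Inputs.** The four grade cells and the tie rule come from Protocol Appendix 5. The T-score cut-offs come from SAP Table 7-1. The age limit comes from Protocol 4.2, which admits subjects from 18 years. Subjects aged 18 to 20 fall on the under-21 line, and everyone else is on the adult line.

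**Mapping.**

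| Finding | Age 21 and over (T- or z-score) | Under 21 (z-score) | SAP Table 7-1 status (T-score) |
|---|---|---|---|
| Above -1.0 | none | none | normal |
| -2.5 to -1.0, no fracture | Grades 1 and 2 both met | Grade 1 | osteopenia |
| Below -2.5, no fracture | none | Grade 2 | osteoporosis |
| Pathological fracture | Grade 3 | Grade 3 | not used |
| Fracture, life-threatening | Grade 4 | Grade 4 | not used |

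**Tie rule.** Bone Mineral Loss is in the clinical part of the scale, so the rule applies. In the second row of the table the adult grade becomes 2, and no adult score leads to Grade 1.

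**Example.** A bone-loss AE with T = -2.0 is Grade 2. One with T = -3.0 and no fracture has no grade.

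**Could this be a table broken in conversion?** That is unlikely. The Grade 2 cell still carries the separate under-21 limit of below -2.5, so both lines are present and distinct. The under-21 line steps from one range to the next with no overlap or gap. The adult line does not.

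**Where it reaches the results.** An adult AE in the overlapping range enters Tables 26, 29 and 32 as Grade 2. An AE below -2.5 enters them only if the site chooses a grade of 2 or more. If severity is left blank, SAP 7.1.2 shows it as missing, and it is not counted as Grade 2, 3 or 4.

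**The case against.** The duplication cannot be disputed. The case on the other side is that little depends on it.

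- **The bone comparison does not use these grades.** The key secondary endpoints are percent changes in hip and spine BMD (Protocol 8.1.3). SAP 7.3.1 takes clinical status from Table 7-1 and sorts decline into percentage categories. SAP 7.3.3 and 7.3.5 count fracture and bone events by preferred term. This stands. A reader might infer that the key secondary comparison of TAF with TDF is distorted, and the documents do not support that.
- **Few events are exposed.** Under Protocol 7.1.3 an abnormal assessment becomes an AE only in certain circumstances, such as association with signs or symptoms. In China, DXA is done only at capable sites, and this SAP covers about 150 subjects. This stands as a limit on size. A reader might size the problem by the share of a reference population in each T-score band. That is a share of people, not a rate of reported AEs, so it says nothing useful here.
- **Events below -2.5 need not be lost.** SAP 7.1.2 covers severity that was not recorded, and nothing says sites will leave it blank. Investigators may enter a grade by judgement, and the lowest ranking applies only to sorting. This also stands. A reader might conclude that osteoporosis AEs will drop out or that reported severity is inverted. The supportable statement is that grading may be inconsistent or blank.
- **SAP Table 7-1 serves another purpose.** It defines BMD status, while Appendix 5 grades AEs, and neither cites the other. A reader might call this a contradiction between the two documents. The inconsistency lies inside Appendix 5, and Table 7-1 is only a useful reference for the -2.5 cut.
- **Grades 1 and 2 share one study-drug instruction** (Protocol 7.5.1), so the overlap changes reporting and not that instruction.

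These points limit the consequence. None of them makes the adult line usable as printed.

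**Conclusion.** The scale is wrong as written for subjects aged 21 and over. Grade 1 bone mineral loss cannot be assigned, the range from -2.5 to -1.0 always yields Grade 2, and a non-fracture AE below -2.5 has no grade.

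The consequence is limited to AE severity: the Grade 2, 3 or 4 summaries in SAP Tables 26, 29 and 32, and the grades shown in listings. An event left ungraded is still counted among all treatment-emergent AEs and, where its term is listed, among bone events. The number of affected events is probably small, but the documents give no rate from which to calculate it.

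This rests on three assumptions: that sites apply the scale and tie rule as printed, that some non-fracture bone-loss AEs are reported, and that the printed cell matches the scale in use. It is an internal-consistency error worth correcting because correction is cheap and the China Week 48 analysis is still ahead.

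**What to change.** 1. In Protocol Appendix 5, reconcile the adult Grade 1 and Grade 2 cells so that they do not overlap and scores below -2.5 are covered. The result should agree with the under-21 line in the same row, where Grade 2 starts below -2.5, and with the -2.5 cut in SAP Table 7-1.
2. Send sites a note explaining the correction.
3. Before the China Week 48 database is finalised, and while treatment is still blinded, query each reported bone-loss AE and ask the investigator to confirm its grade. An SAP rule that re-grades from the T-score is not the right route, because severity is the investigator's assessment under Protocol 7.2 and SAP 7.1.2.
4. State in the report that the non-China Week 48 analysis, which SAP Section 2 says is already done, used the uncorrected scale. The appendix is dated 18 June 2012, so this is very likely, but the sponsor should confirm it.

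The cost is one table cell, a site note, queries on what are probably few events, and a sentence in the report. No new measurements are needed. Scores already exist for subjects who had DXA.

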Appendix Table 1. Protocol Specified Contraceptive Methods

Methods to Use by Themselves	Combination Methods	
	Hormone Methods (choose one and use with a barrier method)	Barrier Methods (use both OR choose one and use with a hormone method)
Intrauterine Devices (IUDs) 
 Copper T 380A IUD LNG 20 IUD 	Estrogen and Progesterone 
 Oral contraceptives Transdermal patch Vaginal ring Progesterone 
 Injection Implant 	
 Diaphragm with spermicide OR Cervical cap with spermicide Male condom (with or without spermicide)
Tubal Sterilization	Partner's vasectomy must be used with a hormone or barrier method.	

The investigator will counsel all subjects on the most effective method(s) for avoiding pregnancy during the study.

4. Contraceptive Requirements for Male Subjects

Male subjects must agree to use protocol specified method of contraception during heterosexual intercourse and avoid sperm donation from the time of the first dose of study drug and throughout the study period, and for at least 30 days after administration of the last dose of study medication

Use of condoms, except for lambskin, has been proven to decrease the risk of transmission of HIV and other sexually transmitted diseases. The use of spermicide is not recommended if the subject or subject's partner is infected with HIV.

5. Procedures to be Followed in the Event of Pregnancy

Subjects will be instructed to notify the investigator if they become pregnant at any time during the study, or if they become pregnant within 30 days of last study drug dose. Subjects who become pregnant or who suspect that they are pregnant during the study must report the information to the investigator and discontinue study drug immediately.

Instructions for reporting pregnancy and pregnancy outcome are outlined in Section [7.6.2.1](#).

Table 3-6.	Analysis Windows for Fasting Glucose, Fasting Total Cholesterol, Fasting Triglycerides, Renal, and Bone Biomarkers	24
Table 3-7.	Analysis Windows for PTH.....	25
Table 3-8.	Analysis Windows for Hepatic Ultrasound	26
Table 3-9.	Analysis Windows for Post-Treatment Assessments except HBV Serology	26
Table 3-10.	Analysis Windows for Post-Treatment HBV Serology	26
Table 7-1.	Normal, Osteopenia, and Osteoporosis as Defined by T-score	44

LIST OF ABBREVIATIONS

AASLD	American Association for the Study of Liver Diseases
AE	adverse event
ALT	alanine aminotransferase (SGPT)
ANCOVA	analysis of covariance
ANOVA	analysis of variance
Anti-HBe	antibody to HBeAg
Anti-HBs	antibody to HBsAg
AST	aspartate aminotransferase (SGOT)
BLQ	below the limit of quantitation
BMD	bone mineral density
BMI	body mass index
bsAP	bone specific alkaline phosphatase
CDER	Center for Drug Evaluation and Research
CG	Cockcroft-Gault
CHB	chronic hepatitis B
CI	confidence interval
CKD-EPI	Chronic Kidney Disease Epidemiology Collaboration formula for calculating glomerular filtration rate
CL _{Cr}	creatinine clearance
CMH	Cochran-Mantel-Haenszel
CRF	case report form
CTX	c-type collagen sequence
CV	coefficient of variation
DMC	data monitoring committee
DNA	deoxyribonucleic acid
DXA	dual-energy x-ray absorptiometry
ECG	electrocardiogram
eCRF	electronic case report form
ED	early discontinuation
eGFR	estimated glomerular filtration rate
ESDD	early study drug discontinuation
FAS	Full Analysis Set
FDA	Food and Drug Administration
FEPO ₄	fractional excretion of filtered phosphate
FEUA	fractional excretion of uric acid
GFR	glomerular filtration rate
Gilead	Gilead Sciences, Inc.
HBeAb	hepatitis B e antibody

HBeAg	hepatitis B e antigen
HBsAb	hepatitis B surface antibody
HBsAg	hepatitis B surface antigen
HBV	hepatitis B virus
HCC	hepatocellular carcinoma
HCV	hepatitis C virus
HDL	high density lipoprotein
HDV	hepatitis D virus
HIV	human immunodeficiency virus
HLGT	high-level group term
HLT	high-level term
IVRS	interactive voice response system
IWRS	interactive web response system
LDL	low density lipoprotein
LLN	lower limit of the normal range
LLT	lower-level term
LOCF	last observation carried forward
M = E	Missing = Excluded
M = F	Missing = Failure
MDRD	Modification of Diet in Renal Disease
MedDRA	Medical Dictionary for Regulatory Activities
MH	Mantel-Haenszel
OC	osteocalcin
P1NP	procollagen type 1 N-terminal propeptide
PBMC	peripheral blood mononuclear cell
PP	per protocol
PT	preferred term
Q	quartile
Q1	first quartile
Q3	third quartile
QD	once daily
RBP	retinol binding protein
SAE	serious adverse event
SAP	statistical analysis plan
SD	standard deviation
SOC	system organ class
TAF	tenofovir alafenamide (Vemlidy®)
TDF	tenofovir disoproxil fumarate (Viread®)
TFLs	tables, figures, and listings
TFV	tenofovir

TFV-DP	tenofovir-diphosphate
TmP	tubular maximum reabsorption rate of phosphate
UACR	urine albumin to creatinine ratio
ULN	upper limit of normal
UPCR	urine protein to creatinine ratio
WHO	World Health Organization

1. INTRODUCTION

GS-US-320-0108 is a randomized, double-blind, noninferiority study to compare the antiviral activity of tenofovir alafenamide (TAF) 25 mg once daily versus tenofovir disoproxil fumarate (TDF) 300 mg once daily for the treatment of HBeAg-negative, chronic hepatitis B (CHB) in treatment-naïve and treatment-experienced subjects. For non-China part, 426 subjects were randomized in a 2:1 ratio to the treatment groups, and were stratified by plasma hepatitis B virus (HBV) DNA level ($< 7 \log_{10}$ IU/mL, $\geq 7 \log_{10}$ IU/mL - $< 8 \log_{10}$ IU/mL, $\geq 8 \log_{10}$ IU/mL) and oral antiviral treatment status (treatment-naïve vs treatment-experienced).

Treatment-naïve subjects are defined as subjects with < 12 weeks of previous oral antiviral treatment with any nucleoside or nucleotide analogue. Treatment-experienced subjects are defined as subjects with ≥ 12 weeks of previous treatment with any nucleoside or nucleotide analogue.

For China, approximately 150 additional subjects (100 in TAF group and 50 in TDF group) will be enrolled for local registration purposes.

The duration of double-blind treatment is 144 weeks (96 weeks under Amendment 1 and 2.1). All subjects who complete the double-blind period of treatment are eligible for participation in the open label TAF 25 mg extension period for an additional 240 weeks (through Week 384/ED). Subjects who already entered open label phase at Week 96 per Amendment 2.1 will continue on open label TAF 25 mg QD through Week 384/ED. For the entire duration of the study, subjects and investigators will remain blinded to the initial treatment regimen to which they were randomized.

This statistical analysis plan (SAP) describes the analysis plan for the Week 48 analysis of subjects enrolled in China only.

1.1. Study Objectives

The primary objectives of this study are as follows:

- To compare the efficacy of TAF 25 mg versus TDF 300 mg once daily for the treatment of hepatitis B e antigen (HBeAg)-negative, CHB at Week 48 in treatment-naïve and treatment-experienced subjects. The primary efficacy parameter is the proportion of subjects with plasma HBV DNA levels below 29 IU/mL
- To compare the safety and tolerability of TAF 25 mg once daily versus TDF 300 mg once daily for the treatment of HBeAg-negative, CHB at Week 48 in treatment-naïve and treatment-experienced subjects

The key secondary safety objectives of this study are as follows:

- To compare the safety of TAF 25 mg once daily versus TDF 300 mg once daily as determined by the percent change from baseline in hip and spine bone mineral density (BMD) at Week 48
- To compare the safety of TAF 25 mg once daily versus TDF 300 mg once daily as determined by the change from baseline in serum creatinine at Week 48
- To compare the safety of TAF 25 mg once daily versus TDF 300 mg once daily as determined by treatment-emergent proteinuria through Week 48

Other secondary objectives of this study are as follows:

- To compare the efficacy of TAF 25 mg once daily versus TDF 300 mg once daily for the treatment of HBeAg-negative, CHB in regard to the proportion of subjects with plasma HBV DNA levels below 29 IU/mL at Week 96, and 144
- To compare the efficacy of TAF 25 mg once daily versus TDF 300 mg once daily for the treatment of HBeAg-negative, CHB in regard to the proportion of subjects with plasma HBV DNA levels below 29 IU/mL (target not detected) at Weeks 48, 96, and 144
- To compare the biochemical (alanine aminotransferase [ALT] normalization) response of TAF 25 mg once daily versus TDF 300 mg once daily for the treatment of HBeAg-negative, CHB at Weeks 48, 96, and 144
- To compare the serological response (loss of hepatitis B surface antigen [HBsAg] with seroconversion to antibody to HBsAg [anti-HBs]) of TAF 25 mg once daily versus TDF 300 mg once daily for the treatment of HBeAg-negative, CHB at Weeks 48, 96, and 144
- To compare the change in fibrosis as assessed by FibroTest[®] of TAF 25 mg once daily versus TDF 300 mg once daily for the treatment of HBeAg-negative, CHB at Weeks 48, 96, and 144
- To compare the incidence of drug resistant mutations of TAF 25 mg once daily versus TDF 300 mg once daily at Weeks 48, 96, and 144
- To compare the change from baseline in ophthalmologic findings by fundoscopic examination of TAF 25 mg once daily versus TDF 300 mg once daily at Weeks 24, 48, 72, 96, and 144 (or ED visit if prior to Week 144 and more than 24 weeks since prior exam) in a subset of subjects
- To characterize the pharmacokinetics of TAF and tenofovir (TFV) and determine intracellular concentrations of tenofovir diphosphate (TFV-DP) within peripheral blood mononuclear cells (PBMCs) in subjects receiving TAF or TDF

- To evaluate the comparative open-label efficacy, safety, and drug resistance mutations of TAF 25 mg QD from Week 96 (Amendments 1 and 2.1) or Week 144 (Amendment 3.1) through Week 384 in subjects initially randomized to TAF 25 mg QD and in subjects sequentially treated with TDF 300 mg QD for 96 weeks (Amendments 1 and 2.1) or for 144 weeks (Amendment 3.1) and then switched to open-label TAF 25 mg QD
- To compare the safety and tolerability of TAF 25 mg once daily versus TDF 300 mg once daily for the treatment of HBeAg-negative, CHB beyond Week 48 during the double-blind phase in treatment-naïve and treatment-experienced subjects

